15.3 Statistical Methods

Descriptive statistics and two-sided 95% confidence intervals will be presented for the effectiveness and safety endpoints. No formal statistical hypothesis and inferential statistics will be formulated and performed. Analyses of all endpoints will be performed in the proposed analysis populations excluding the subjects with missing outcomes.

15.3.1 Safety

Acute safety outcome will be reported as the number of primary adverse events and the number of subjects experiencing primary adverse events (within 7 days of procedure, with exception for PV stenosis and AE fistula (Table 14.4).

Incidence of (S)AEs during follow-up will be reported as the number of (S)AEs and the number of subjects experiencing (S)AEs. The number and percentage of subjects with (S)AEs will be summarized overall and by AE type, seriousness, severity, causality, anticipated or not and outcome. Listing of (S)AEs will also be provided.

The safety population (SP) will be used as the analysis population.

15.3.2 Effectiveness

Effectiveness outcomes includes freedom from documented AF/AT/AFL recurrence post the 3-month blanking period through the 12-month follow up, conversion of atrial fibrillation to normal sinus rhythm or atrial tachycardia post CFGA or post overall ablation procedure with or without cardioversion, and entrance block confirmation post PVI. The number and percentages of subjects with effectiveness endpoints and the corresponding two-sided 95% binomial confidence intervals will be presented. Listing of effectiveness outcomes will be provided.

The evaluable population (EP) will be used as the analysis population for all effectiveness endpoints.

15.3.3 Investigational Device Performance

Investigational device performance will be reported as the number of ablation targets identified and the maximum % of active electrodes. Investigational device performance will also be reported by means of survey questions. Listings of survey answers/scoring will also be provided. These analyses will be conducted in the evaluable population (EP).

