6.3.1 Baseline Mapping Sequence

All eligible subjects will undergo the CARTOFINDER™ Mapping Procedure, using the RF-192 catheter. The subject must be in AF prior to the insertion of the RF-192 Mapping catheter. If the subject is not in AF at the time of the procedure the patient will be regarded as discontinued per inclusion criteria, followed for 7-days post-procedure and exited from the study.

- Standard Fast Anatomic Mapping (FAM) procedure of the Right Atria (RA) using the THERMOCOOL SMARTTOUCH™ or SMARTTOUCH® SF Catheter.
- Baseline CARTOFINDER™ map, recording of the RA using the RF-192 catheter
 - On deployment of the RF-192 catheter, the basket catheter will be placed in optimal position to maximize contact with the RA wall
 - Once the catheter's position is confirmed and contact is optimal, the investigator will obtain intra-cardiac signals
 - One 30 second recording will be obtained

DO NOT perform any RA ablations at this point

- Transseptal Puncture
- Standard FAM of the Left Atria (LA) using the THERMOCOOL® SMARTTOUCH™ or SMARTTOUCH® SF Catheter.
- Baseline CARTOFINDER™ map, recording of the LA using the RF-192 catheter
 - On deployment of the RF-192 catheter, the basket catheter will be placed in optimal position to maximize contact with the LA wall
 - Once the catheter's position is confirmed and contact is optimal, the investigatorinvestigator will obtain intra-cardiac signals
 - One 30 second recording will be obtained

RF192 catheter must not remain in the subject (being deployed in the atrium) for cumulative duration greater than 1.5 hours (90 mins)

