6.4 Analysis of the CARTOFINDER™ Baseline Map

After completion of the CARTOFINDER™ baseline mapping procedure, the CARTOFINDER™ maps will be

processed and analyzed for the presences of ablation targets including FI/RAPs by the treating/ablating investigator who has been trained by Biosense Webster personnel knowledgeable in analyzing CF maps and the operation of the CARTOFINDER™ system.

Ablation Targets (FI/RAP) identification:

- Identify areas with ablation targets including focal impulse (FI) or repetitive activation patterns (RAPs)
 - If an ablation target is identified, the subject will receive CFGA followed by PVI
 - If no CF ablation target is identified, the subject will be treated per standard of care and exits the study after 7 day follow up.

No RF ablation should occur prior to analysis of the CARTOFINDER™ Maps.

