11 SUBJECT DISPOSITION

The following subject groups are defined:

- **Enrolled Subjects:** Subjects who have signed and dated the Informed Consent Form.
- **Excluded Subjects:** Enrolled subjects who have signed an ICF but are found not meeting eligibility criteria prior to insertion of the RHYTHMFINDER™ 192 Catheter.
- **Mapping Failure:** Enrolled subjects who have the RHYTHMFINDER™ 192 Catheter inserted and where inability to record baseline CF mapping signals is observed, will be followed up for 7-days.

If an SAE is reported for a mapping failure subject, they will be followed until event resolution or stabilized. The investigator will document mapping failures in the electronic CRF, including reasons for failure.

- **Discontinued Subjects:** Enrolled subjects who have the RHYTHMFINDER™ 192 Catheter inserted but do not undergo CF guided ablation. If subject's arrhythmia is determined at the time of EP study to be a non-study arrhythmia (required for subject enrollment per study inclusion criteria), the subject will be categorized as discontinued subject. Discontinued subjects will remain in follow-up for 7-days. If an SAE is reported for a discontinued subject, they will be followed until event resolution or stabilized.
- **Lost to Follow-up Subjects:** Subjects who are enrolled and have the RHYTHMFINDER™ 192 Catheter inserted, but contact is lost after most recent follow-up visit (despite 3 documented attempts to contact the subject).
- **Withdrawn / Early Termination Subjects:** Subjects who have RHYTHMFINDER™ 192 Catheter inserted but withdraw consent for study participation or are withdrawn by the investigator or are terminated from the study prior to completion of all follow-up visits
- **Completed Subjects:** enrolled subjects who complete the last scheduled follow-up visit per study protocol.

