15.2 Analysis Populations

The following analyses populations will be used to complete the analyses of the data:

Safety Subject Population: The safety subject population will include all enrolled subjects who have the RHYTHMFINDER™ 192 Catheter inserted, regardless if cartofinder guided ablation was performed

Evaluable Subject Population: The evaluable subject population will include all enrolled subjects who have the RHYTHMFINDER™ 192 Catheter inserted and where cartofinder guided ablation was performed

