The descriptive statistics for pre-CFGA, post-CFGA and post-PVI cycle length will be presented. The changes from pre-CFGA cycle length at each ablation procedure steps (post-CFGA and post-PVI) will also be summarized

The EP and EffP will be used as the analysis population for all effectiveness endpoints.

- Other Study Assessments
 - AAD use post the 3-month blanking period
 - Incidence of repeat ablation procedures for AF post the 3-month blanking period

The descriptive statistics for the above endpoints will be summarized in EP.

- Investigational Device Performance

Investigational device performance will be reported as the number of ablation targets identified and the maximum % of active electrodes. Investigational device performance will also be reported by means of survey questions. Listings of survey answers/scoring will also be provided.

- Procedural Data

Procedural data including but not limited to procedure duration, mapping duration, fluoroscopy time, RF application time, number of RF application, power, contact force, impedance, temperature, and location of ablation targets will be summarized with descriptive statistics and listed.

These analyses will be conducted in the EP.

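### Device performance is summarised only in subjects who had guided ablation, so failed maps and no-target maps are left out and no explicit target yield is specified in the protocol or SAP text

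*Protocol*

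**What the plan says.** Protocol 15.3.3 lists three device-performance outputs: the number of ablation targets identified, the maximum percentage of active electrodes, and an investigator survey. It then fixes the analysis set: "Listings of survey answers/scoring will also be provided. These analyses will be conducted in the evaluable population (EP". In SAP 10.4 the sentence "These analyses will be conducted in the EP" comes after the procedural-data item. Whether it covers device performance as well or procedural data alone, the SAP names no other set for device performance.

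Protocol 15.2 defines the evaluable population (EP) as subjects with the catheter inserted and "where cartofinder guided ablation was performed". The Safety Population (SP) is wider: catheter inserted, with or without guided ablation.

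Two groups have the catheter inserted but do not reach guided ablation under the protocol:

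- **No-target maps.** Protocol 6.4: "If no CF ablation target is identified, the subject will be treated per standard of care", with exit after the 7-day follow-up.
- **Mapping failures.** Protocol section 11: catheter inserted, "where inability to record baseline CF mapping signals is observed".

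SAP 10.2 summarises disposition for all enrolled subjects, with Mapping Failure as a named category. No-target subjects have no category of their own. They fall under Discontinued, defined as subjects with the catheter "inserted but do not undergo CF guided ablation", together with non-study arrhythmias. The table shells cited in the SAP appendix are a separate document that was not available.

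**The concern.** Protocol section 3 says the study will assess mapping data and mapping-catheter functionality. Section 5 says it serves to show how well the system generates maps for guiding ablation and how well the investigator acquires signals with the catheter. A summary restricted to subjects whose map succeeded, showed a target and led to ablation describes the device given that it worked. It does not describe how often it worked.

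The restriction also has no measurement reason for electrodes. Protocol 4.2 defines that measure at the initial mapping procedure, before any ablation, so it is the same quantity in every subject mapped. Protocol 18.1 names missing information from insufficient catheter contact as a risk. The EP summary cannot show whether no-target maps had fewer active electrodes, or whether failed or no-target maps received lower survey scores.

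What is at stake is the feasibility reading of the study, which is descriptive and has no hypothesis.

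**Working it through.** **1. Plan's own figure.** There is none to reproduce. The plan states no mapping success rate, target yield or precision, and the range 40-70 is given without a formula.

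**2. What the EP can show.** EP membership requires guided ablation, and guided ablation per protocol requires a baseline target. Yield in the EP is therefore 40/40 or 70/70. The nominal exact 95% intervals (91.2-100% and 94.9-100%) carry no information. The baseline target count per subject cannot be zero in subjects treated per protocol.

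**3. Illustration.** Let f be the mapping-failure rate and t the no-target rate, both per insertion. Both are assumptions. Suppose also that every subject with a target is ablated and that no non-study arrhythmia appears after insertion. Then:

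- insertions needed = EP / (1 - f - t), rounded up
- mapped = insertions × (1 - f), rounded
- left out of the device summary = insertions - EP

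With f = t = 10% and Clopper-Pearson 95% intervals:

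| | EP 40 | EP 70 |
|---|---|---|
| Insertions | 40/0.8 = 50 | 70/0.8 = 87.5, so 88 |
| Left out | 10 | 18 |
| Recorded map per insertion | 45/50 = 90.0% (78.2-96.7) | 79/88 = 89.8% (81.5-95.2) |
| At least one target per insertion | 40/50 = 80.0% (66.3-90.0) | 70/88 = 79.5% (69.6-87.4) |
| At least one target per mapped subject | 40/45 = 88.9% (75.9-96.3) | 70/79 = 88.6% (79.5-94.7) |

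Counting zero for a recorded map without a target, the mean target count per mapped subject is 40/45 = 0.889 of the EP mean, about 11% lower whatever that mean is.

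**4. Range, and the two readings of 40-70.** Protocol 15.1 and SAP section 8 call the 40-70 subjects evaluable. The Protocol Synopsis, Protocol section 5 and SAP section 1 call them enrolled. With f and t each from 5% to 20%:

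- *Evaluable reading.* EP 40 needs 40/0.90 to 40/0.60, that is 45 to 67 insertions, with 5-27 left out. EP 70 needs 78 to 117, with 8-47 left out.
- *Enrolled reading.* Insertions cannot exceed about 70. Left out = insertions × (f + t), from 40 × 0.10 = 4 to 70 × 0.40 = 28. At f = t = 10%, yield per insertion is 32/40 = 80.0% (64.4-90.9%) or 56/70 = 80.0% (68.7-88.6%).

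**5. What planned output already gives.** No-target count ≈ SP - EP - mapping failures. In the first example, 50 - 40 - 5 = 5. This is exact only if nobody has a non-study arrhythmia found after insertion and nobody has a target that is left unablated.

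**The case against.** The strongest reply is that most of this can be recovered. SP and EP are both defined, mapping failures are counted in disposition, and the no-target number follows by subtraction. AF is required before the catheter goes in (Protocol 6.3.1), which limits later non-study arrhythmias. The measures are listed as other assessments in a study without hypotheses.

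Much of that stands. A reader might infer that mapping failures vanish from the report, or that the no-target count is lost. The documents support neither. What remains is that the subtraction is approximate and no text asks for it. Discontinued, as worded, also covers every mapping failure, so the disposition totals do not separate the groups. Subtraction recovers counts only; it gives no electrode or survey results for the subjects left out.

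Three further limits are fair:

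- For electrodes, widening the set mainly adds the no-target maps, because a mapping failure by definition has no recorded baseline signals.
- Inclusion criterion 5 requires enough left atrial electrical activity to identify targets. Some no-target subjects may therefore be eligibility failures, and a yield reflects patient selection as well as the device.
- The unseen table shells may contain a no-target count. They would not change the analysis set that Protocol 15.3.3 fixes.

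**Conclusion.** The concern holds as a reporting gap that should be closed. The EP restriction in Protocol 15.3.3 is explicit and leaves out every mapping failure and, under the protocol flow, every no-target map. Target yield is then 100% by construction, so the device summary cannot by itself support the mapping aims in sections 3 and 5. The statement that no explicit no-target count or yield is specified applies to the protocol and SAP text only.

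The size is unknown, because the documents give no rates. At an assumed 10% for each rate, 10 of 50 insertions are left out for 40 evaluable subjects. Across 5-20% for each, the number left out is 5-47 if 40-70 means evaluable and about 4-28 if it means enrolled.

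Two stronger inferences are not supported. The first is that the EP figures for electrodes and survey are biased in the device's favour: the direction is unknown, since a no-target map need not mean poor contact or device failure. The second is that the study's effectiveness or safety results are affected: safety is analysed in the SP, and no listed effectiveness or safety endpoint changes. How subjects found not in AF before insertion are classified is a separate matter, since they have no map.

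**What to change.** In Protocol 15.3.3 and SAP 10.4:

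1. Report the survey and the maximum percentage of active electrodes in the Safety Population using available data. Show the number of subjects with data, and give no electrode value where no signal was recorded.
2. Report the number of baseline targets in all subjects with a recorded baseline map, counting zero for a map without a target and no value for a mapping failure. Keep the EP summary, labelled as conditional on guided ablation.
3. Report with exact 95% intervals the proportion of insertions with a recorded baseline map, and the proportion with at least one target among insertions and among mapped subjects. State whether a recording from one atrium is enough to count as mapped.
4. Make the post-insertion categories in Protocol section 11 and SAP 10.2 mutually exclusive: mapping failure, non-study arrhythmia, recorded map without a target, target identified but not ablated, guided ablation.

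Other procedural data can stay in the EP. The cost is a few table rows and a check that the eCRF captures these items for every insertion. Protocol 7.1 lists them without limiting them to ablated subjects, and reasons for mapping failure are already recorded. The reported target count and yield will be less favourable than the EP figures whenever a failure or no-target map occurs.

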15.3.4 Procedural Data

Procedural data such as procedure duration, mapping duration, fluoroscopy time/dose, power, contact force, will be summarized with descriptive statistics and listed. These analyses will be conducted in the evaluable population (EP).

15.4 Missing Data Handling

Missing data will be queried for reasons and will not be imputed.

16 ADMINISTRATIVE PROCEDURES AND RESPONSIBILITIES

The clinical investigation will be conducted in compliance with this protocol, and according to ISO 14155: 2011, MEDDEV 2.7/3, the medical device directive 93/42/EC and amendments, the Declaration of Helsinki, the International Conference on Harmonization (ICH) Harmonized Tripartite Guideline of Good Clinical Practice (E6) and in compliance with national regulations.

16.1 Research Ethics Board/Institutional Review Board/Ethics Committee

This protocol and the informed consent must be reviewed and approved by the appropriate REB/IRB/EC and the Competent Authorities/Health Authorities where the clinical investigation is to be conducted before enrollment of subjects. Any additional requirements imposed by the REB/IRB/EC or regulatory authority shall be followed, if appropriate. The sponsor and the REB/IRB/EC must approve in writing any changes to the protocol that affect the rights, safety, or welfare of the subjects, or may adversely affect the validity of the clinical investigation.

A signed copy of the REB/IRB/EC Approval Form and a signed copy of the REB/IRB/EC approval letter addressed to the investigator must be submitted to the sponsor certifying clinical investigation approval before commencement of subject enrollment. Investigators are responsible for submitting and obtaining initial and continuing review (per local regulations) of the clinical investigation by their REB/IRB/EC.

16.2 Monitoring of the Study

Monitoring will be conducted throughout the course of this study according to the Monitoring Plan and sponsor standard operating procedures.

Monitoring visits will be conducted to oversee the progress of the study and verification of the following:

- the rights and wellbeing of the subjects are protected;
- the study is conducted according to Good Clinical Practices (GCP) and local regulations;
- the protocol and applicable amendments are followed;
- the recorded data are accurately represented.

The sponsor and/or designee will perform on-site monitoring visits as defined in the study Monitoring Plan. Each visit will encompass activities such as verification that all subjects have signed the study's ICF, confirmation that procedures are being followed, completion of appropriate source document verification, anonymized CARTO files downloads, and identification of and action taken to resolve any issues or problems with the study.

The sponsor may request further documentation such as investigator and/or EP lab procedure notes when needed or when complications or device deficiencies are observed. To this end, the investigator and institution must permit inspection of the study files and subjects' eCRFs by Sponsor personnel.

16.3 Management of Protocol Amendments

All instructions described in this study protocol are to be followed. If an amendment is required, it must be made in written form and receive approval from all persons and authorities who approved the original protocol. Administrative changes (do not effect subjects benefits/risks ratio) may be inserted with abbreviated approval. All amendments will be distributed to all original protocol recipients.

16.4 Adherence to the Protocol

The investigator is responsible for ensuring the clinical investigation is conducted in accordance with the procedures and evaluations described in this protocol (see Investigator Signature Page at the beginning of this protocol).

Deviations from the protocol shall not be made except in a medical emergency, when the intent is to reduce immediate risk to the subject. In such cases, the sponsor, REB/IRB/EC, regulatory authorities, and insurance company, as appropriate, should be notified in accordance with local requirements. Changes to the protocol may be made only when a written protocol amendment provided by the sponsor has been signed by the investigator and approved by the REB/IRB/EC and applicable regulatory agencies in accordance with local requirements and ISO 14155.

The sponsor is responsible for submitting progress reports, including safety summary and deviations, when requested, to all reviewing ECs and the regulatory authorities.

16.5 Records and Responsibilities

16.5.1 Study Early Termination, Suspension of the Study

The sponsor may suspend or prematurely terminate either the study in an individual study site or the entire study for significant and documented reasons including any significant and documented reasons as deemed appropriate by the sponsor.

A principal investigator, REB/IRB/EC, or regulatory authority may suspend or prematurely terminate participation in the study at the study sites for which they are responsible.

If suspicion of an unacceptable risk to subjects arises during the study, or when so instructed by the REB/IRB/EC or regulatory authorities, the sponsor shall suspend the study while the risk is assessed. The sponsor shall terminate the study if an unacceptable risk is confirmed.

The sponsor shall consider terminating or suspending the participation of a particular study site or investigator in the study if monitoring or auditing identifies serious or repeated deviations on the part of an investigator.

If suspension or premature termination occurs, the terminating party shall justify its decision in writing and promptly inform the other parties with whom they are in direct communication. The principal investigator and sponsor shall keep each other informed of any communication received from either the REB/IRB/EC or the regulatory authority.

If, for any reason, the sponsor suspends or prematurely terminates the study at an individual study site, the sponsor shall inform the responsible regulatory authority as appropriate and ensure that the REB/IRB/EC is notified, either by the principal investigator or by the sponsor. If the suspension or premature termination was in the interest of safety, the sponsor shall inform all other principal investigators.

If suspension or premature termination occurs,

- a. the sponsor shall remain responsible for providing resources to fulfill the obligation from the Protocol and existing agreements for following up the subjects enrolled in the study, and
- b. the principal investigator or authorized designee shall promptly inform the enrolled subjects at his/her study site, if appropriate, and
(Note: the method and the timing of this communication will depend on the circumstances and the perceived risks)
- c. arrangements will be made for the return of all devices supplied and other material in accordance with the sponsor procedures for the study

When the sponsor concludes an analysis of the reason(s) for the suspension, implements the necessary corrective actions, and decides to lift the temporary suspension, the sponsor shall inform the principal investigators, the REB/IRB/ECs, and, where appropriate, the regulatory authority of the rationale and provide them with the relevant data supporting this decision.

Concurrence shall be obtained from the REB/IRB /ECs and, where appropriate, regulatory authorities before the study resumes.

If subjects have been informed of the suspension, the principal investigator or authorized designee shall inform them of the reasons for resumption.

In case of early termination of the clinical investigations, the sponsor or his authorized representative as applicable will notify the relevant regulatory agencies , competent authorities and EC of the end of the clinical investigation, with a justification in case of early termination. In the case of early termination of the clinical investigation on safety grounds this notification shall be communicated to all concerned regulatory agencies competent authorities and REB/IRB /EC's as applicable and directed by the Medical Device Directive 93/42/EC and amendments

